3.2 Bicalutamide (Casodex®) (NSC-722665)

For bicalutamide, goserelin acetate, and leuprolide acetate, commercially

Available preparations are used as per the FDA approved dose, route and schedule. Information about commercial drugs is publicly available in the Physician's Desk Reference (PDR), prescribing information and other resources.

Chemistry: Bicalutamide is a racemic mixture containing two enantiomers, (2RS)-4'-Cyano-3(4-fluorophenylsulphonyl)-2-hydroxy-2-methyl-3'-trifluoromethyl propionanilide. Bicalutamide is an active non-steroidal antiandrogen and its antiandrogen activity resides exclusively in the (-) or (R) enantiomer. Unlike flutamide, it is peripherally selective and does not cause a rise in serum LH or Testosterone in male rats and dogs. This peripheral selectivity may be because it penetrates poorly the CNS and Hypothalamus (the site of negative feedback of androgens). In humans, rises in LH, Testosterone and Estradiol concentrations were seen. These rises were not dose related. In 90%, testosterone levels remained within normal limits. There was no significant rise in mean serum FSH.

Bicalutamide has been given to over 3,500 men in 35 different clinical studies worldwide, in doses up to 600 mg daily.

Adverse Effects:

When bicalutamide is given in combination with an LHRH analog, the pharmacologic adverse event profile is dominated by the LHRH analog and includes hot flashes (53%), gynecomastia (9%) and breast pain (6%). Other adverse events reported regardless of causality included diarrhea (12%), constipation (22%), nausea (15%) and abdominal pain (11%). Other adverse events were reported, such as fatigue (22%), pain (35%), back pain (25%), pelvic pain (21%), infection (18%), peripheral edema (13%), dyspnea (13%), nocturia (12%), hematuria (12%), anemia (11%), dizziness (10%). Bicalutamide has been associated with changes in liver function, although these are infrequent (7%) and rarely occur with jaundice.

Many of these changes improved or resolved despite continuation of bicalutamide therapy. There have been no reports of fatal hepatotoxicity associated with bicalutamide therapy.

Pharmacology

Pharmacokinetics:

Animal studies: After oral single dose administration, absorption of the compound was slow with peak concentration occurring 3 - 12 hours and plateau between 2 and 48 hours. There was nonproportional increase in plasma levels with increasing doses. Elimination half life ranges from 17 - 28 hours in male rats, 21 - 29 hours in female rats and 5 - 7.5 days in dogs. 91 - 96% of bicalutamide is bound to plasma protein.

Human studies: After single doses, mean time for peak plasma concentration was 6 hours at 10 and 30 mg, but at 50 mg, it was 16 hours. Mean plasma elimination half-lives after 12 weeks of 10, 30, 50, 100 mg/day was 7 - 10 days. This finding was consistent with single dose data. In patients given daily doses of 50 mg, mean plasma concentration was 10 ug/ml at 12 weeks. After single doses, there was linear increase with doses between 10 and 50 mg, but became non-linear at doses of 50 - 100 mg. At 100 mg, the oral bioavailability is reduced by 30% but plasma elimination half-life is unchanged. Bicalutamide is extensively metabolized and metabolites are excreted by both the biliary and urinary system.

Formulation: Bicalutamide is prepared as round, film-coated green or white tablets containing standard recipients and 50 mg of the drug.

Storage and stability: All packages of bicalutamide should be stored securely in a dry place at room temperature.

Route of Administration: Bicalutamide is to be administered in tablet form as a 50 mg once-daily oral dose. Patients should be instructed to take one tablet once daily.

3.3 Gonadotropin/Luteinizing Hormone Releasing Hormone (GNRH/LHRH) analogues: The commonly used preparations are listed below. However any of the other preparations with FDA approval that result in androgen suppression are acceptable.

Goserelin acetate implant (Zoladex®) / Leuprolide (Lupron)

a. PHARMACOLOGY

Mechanism of Action: Following initial administration in males, goserelin causes an initial increase in serum luteinizing hormone (LH) and follicle stimulating hormone (FSH) levels with subsequent increases in serum levels of testosterone.

Chronic administration of goserelin leads to sustained suppression of pituitary gonadotropins, and serum levels of testosterone consequently fall into the range normally seen in surgically castrated men approximately 2-4 weeks after initiation of therapy.

b. PHARMACOKINETICS

1. *Absorption:* Goserelin 3.6 mg is released slowly in first 8 days, and then rapid and continuous release for the remainder of the 28 day dosing period. Time to peak concentration for goserelin 3.6 mg is 12-15 days in males and 8-22 days in females. Goserelin 10.8 mg exhibits an initial rapid release resulting in a peak concentration at 2 hours after dosing. From Day 4 until the end of the 12-week dosing interval, the sustained release of goserelin produces a reasonably stable systemic exposure.

2. *Distribution:* Apparent volumes of distribution determined after subcutaneous administration of 250 mcg aqueous solution of goserelin were 44.1 and 20.3 liters for males and females, respectively. Goserelin is approximately 27% protein bound.

3. *Metabolism:* Metabolism of goserelin by hydrolysis of the C-terminal amino acids is the major clearance mechanism. The half-life elimination ($t_{1/2}$) is approximately 4 hours in males and 2 hours in females

4. *Elimination:* Clearance of goserelin is very rapid and occurs primarily via urinary excretion (>90%; 20% as unchanged drug).

c. ADVERSE EFFECTS

1. Refer to the package insert or manufacturer website for the most complete and up to date information on contraindications, warnings and precautions, and adverse reactions.

Side Effects

Adverse events associated with the use of Leuprolide/Goserelin may include, but are not limited to, the following:

- hot flashes
- injection site reactions
- weight gain
- increase in liver enzymes
- tiredness
- hypertension
- back and joint pain
- chills
- urinary tract infection
- decreased sex drive and trouble with erectile function

Adverse effects occurring in <1%, postmarketing, and/or case reports:

1. ALT increased, anaphylaxis, AST increased, diabetes, glucose tolerance decreased, hypercalcemia, hypercholesterolemia, hyperlipidemia, hypersensitivity reactions, hypotension, ovarian cyst, pituitary apoplexy, psychotic disorders, urticaria.
2. Pregnancy and Lactation: Not applicable as this study only enrolls male patients. Pregnancy category X in patients with endometriosis and endometrial thinning. Pregnancy category D in patients with advanced breast cancer. It is not known if goserelin is excreted in human milk, however goserelin is excreted in the milk of lactating rats.
3. Drug Interactions: Luteinizing hormone-releasing hormone analogs may diminish the therapeutic effect of antidiabetic agents. No formal drug-drug interaction studies have been performed. Please refer to the current FDA-approved package insert for additional information.
4. The FDA issued a safety communication in October 2010 based on their ongoing safety review of LHRH agonists. The safety communication discusses the potential for an increased risk of diabetes and cardiovascular disease (myocardial infarction, sudden cardiac death, stroke) associated with these agents. The risk is thought to be low in men receiving LHRH agonists for prostate cancer. In this trial, LHRH agonists are being administered for a short period of time. FDA recommendations include management of cardiovascular risk factors according to current standards of practice.

d. DOSING & ADMINISTRATION

1. Dosing – See Package Insert of preparation used.
2. Goserelin is administered subcutaneously into the anterior abdominal wall below the navel line using aseptic technique.

e. STORAGE & STABILITY

Refer to the current FDA-approved package insert for storage, stability and special handling information.

f. HOW SUPPLIED

1. Goserelin acetate implant is available in a 3.6 mg or 10.8 mg disposable syringe device. The unit is sterile and comes in a sealed, light- and moisture-proof, aluminum foil laminate pouch containing a desiccant capsule.
2. Goserelin is commercially available and will not be supplied. Refer to the current FDAapproved package insert for additional information.

Leuprolide (Eligard®, Lupron Depot®) (NSC-377526)

PHARMACOLOGY

Mechanism of Action: Leuprolide inhibits gonadotropin secretion by acting as a luteinizing hormone-releasing hormone (LHRH) agonist. Continuous administration results in suppression of ovarian and testicular steroidogenesis due to decreased levels of LH and FSH with subsequent decrease in testosterone (male) and estrogen (female) levels. In males, testosterone levels are reduced to below castrate levels. Leuprolide may also act directly on the testes as well as act by a different mechanism not directly related to reduction in serum testosterone.

DOSING & ADMINISTRATION

1. Dosing – Per package insert. Typically 7.5 mg monthly or 22.5 mg every 3 months
2. Leuprolide is administered intramuscular (Lupron Depot®) or subcutaneous (Eligard®) injection based on commercial depot formulation. Injection sites should be varied periodically.

STORAGE & STABILITY

Refer to the current FDA-approved package insert for storage, stability and special handling information.

HOW SUPPLIED

1. Leuprolide acetate is available in 3.75 mg, 7.5 mg, 11.25 mg, 22.5 mg, 30mg, or 45 mg depot formulation kit with accompanying diluent. The prefilled dual chamber syringe contains lyophilized microspheres of leuprolide acetate incorporated in a biodegradable lactic acid polymer.
2. Leuprolide/Goserelin is commercially available and will not be supplied.

Other LHRH agents can be utilized per the FDA approved dose and schedule. GNRH antagonists cannot be used.

4.0 ELIGIBILITY CRITERIA

4.1 Inclusion Criteria:

1. Histologically confirmed prostate adenocarcinoma with metastasis either starting or recently started on LHRH analogue therapy. [Late induction permitted within 3 months of starting LHRH analogue therapy or antiandrogen] All patients who have not initiated hormone therapy (Early induction patients) must have elevated PSA ≥ 4 ng/ml within 28 days prior to registration. For late induction registrations, PSA must be ≥ 4 ng/ml prior to start of androgen deprivation therapy; either antiandrogen or LHRH analogue or GNRH antagonist .If patients are on antiandrogen, this will need to be discontinued for at least 7 days prior to registration.
2. Patients with a history of prior neoadjuvant or adjuvant hormone therapy are eligible provided they have received twenty four or less months of hormone treatment (single or combination treatment, excluding orchiectomy). Neoadjuvant/adjuvant hormone therapy must have been discontinued at least 6 months prior to registration. This is intended to exclude patients who might have been rendered indirectly androgen insensitive.
3. There must be no plans to receive concomitant chemotherapy, biological response modifiers, radiation therapy or hormonal therapy. Concomitant radiation therapy is allowed for the palliation of severe pain/neuropathic compression.
4. Prior or concomitant use of megestrol acetate for the treatment of hot flashes is allowed.
5. Patients must have a performance status of 0 - 2 by Zubrod Criteria.
6. Patients must have recovered from any major infections and/or surgical procedures and, in the opinion of the investigator, not have significant active medical illness precluding protocol treatment or survival.
7. No prior malignancy is allowed except for adequately treated basal cell (or squamous cell) skin cancer, superficial or in situ cancer of the bladder. For an invasive cancer the patients should be disease free for at least 3 years prior to enrollment on study.
8. For all patients a bone scan must be performed within 60 days prior to registration for tumor assessment. CT scans (abdomen and pelvis) and chest x-ray are optional, but must be repeated if used for disease assessment. For late induction registrations, tumor assessment imaging showing metastatic disease must be available prior to start of androgen deprivation therapy.
9. Age 18 or older and willing and able to provide informed consent.
10. Willingness to swallow pills and no medical condition that would interfere with this.
11. Male patient and his female partner who is of childbearing potential must use 2 acceptable methods of birth control (one of which must include a condom as a barrier method of contraception) starting at screening and continuing throughout the study period and for 3 months after final study drug administration. Patients are also required to use a condom if having sex with a pregnant woman.
12. Patient should agree to a tumor tissue biopsy prior to protocol enrollment. Post therapy biopsy is optional.
13. Patients who are being treated with a GNRH antagonist should be willing to switch to a LHRH analogue after registration.
14. Patients must have one of the following a) Low volume disease (defined as no visceral metastases and < 4 bone metastases) or b) are not candidates for docetaxel based chemotherapy or 3) refused docetaxel chemotherapy

4.2 Patients must NOT meet any of the following exclusion criteria:

1. History of seizure or any condition that may predispose to seizure (e.g., prior cortical stroke, significant brain trauma) at any time in the past. Also, history of loss of consciousness or transient ischemic attack within 12 months of Day 1 visit;
2. Known or suspected brain metastasis or active leptomeningeal disease;
3. Severe concurrent disease, infection, or co-morbidity that, in the judgment of the Investigator, would make the patient inappropriate for enrollment;
4. Absolute neutrophil count < 1,000/ μ L, or platelet count < 50,000/ μ L, or hemoglobin < 8 /dL) at the Screening visit.
5. Total bilirubin, alanine aminotransferase (ALT) or aspartate aminotransferase (AST) > 2.5 times the upper limit of normal
6. Creatinine > 177 μ mol/L (2 mg/dL)
7. Clinically significant cardiovascular disease including:
 - Myocardial infarction within 6 months;
 - Uncontrolled angina within 3 months;
 - Congestive heart failure New York Heart Association (NYHA) class 3 or 4, or patients with history of congestive heart failure NYHA class 3 or 4 in the past, unless screening echocardiogram or multi-gated acquisition scan performed within 3 months results in a left ventricular ejection fraction that is \geq 45%;

---History of clinically significant ventricular arrhythmias (e.g., ventricular tachycardia, ventricular fibrillation, torsades de pointes);

---History of Mobitz II second degree or third degree heart block without a permanent pacemaker in place;

---Hypotension as indicated by systolic blood pressure < 86 millimeters of mercury (mmHg) at the Screening visit;

---Bradycardia as indicated by a heart rate of < 50 beats per minute on the Screening ECG;

---Uncontrolled hypertension as indicated by systolic blood pressure > 170 mmHg or diastolic blood pressure > 105 mmHg
8. Gastrointestinal disorder affecting absorption (e.g., gastrectomy, active peptic ulcer disease within last 3 months);
9. Treatment with concurrent 5- α reductase inhibitors (finasteride, dutasteride), estrogens, and/or cyproterone
10. Treatment with systemic biologic therapy for prostate cancer (other than approved bone targeted agents and GnRH-analogue therapy) or other agents with anti-tumor activity within 4 weeks of enrollment (Day 1 visit);
11. History of prostate cancer progression on ketoconazole;
12. Prior use, or participation in a clinical trial, of an investigational agent that blocks androgen synthesis (e.g., abiraterone acetate, TAK-700, TAK-683, TAK-448) or agents that block the androgen receptor (e.g., ARN-509)
13. Previous enzalutamide therapy;
14. Use of an investigational agent within 2 weeks of enrollment (Day 1 visit);

15. Use of herbal products that may have hormonal anti-prostate cancer activity and/or are known to decrease PSA levels (e.g., saw palmetto) or systemic corticosteroids greater than the equivalent of replacement steroids or > equivalent of 10 mg of prednisone per day within 4 weeks of enrollment (Day 1 visit);
16. Any condition or reason that, in the opinion of the Investigator, interferes with the ability of the patient to participate in the trial, which places the patient at undue risk, or complicates the interpretation of safety data.
17. Prior chemotherapy for metastatic disease.
18. ≥30 days of antiandrogen therapy monotherapy without androgen deprivation therapy.
19. Life expectancy of 6 months or less.

5.0 TREATMENT PLAN:

5.1 Patient Registration and Data Collection:

All patients shall be registered with the Cancer Center Clinical Trials Office at [contact] ([name]).

At the time of registration, a pre-study form and all information required to verify eligibility shall be necessary on each patient prior to treatment. This form should be faxed to [contact] and eligibility verification will be sent within 48 hours. Data will be collected and maintained on study specific electronic case report forms in the Oncore Research Enterprise system at

Karmanos Cancer Institute. Training and support will be provided for all staff entering data. Data entry must occur within 2 weeks of visits along with submission of applicable source documentation. The only concomitant medication data to be submitted is administration of bisphosphonate or denosumab.

5.2 Stratification and randomization procedures:

The registering data manager will first stratify the patient by race (AA or other) and cancer related bone pain at diagnosis of metastatic disease (present or absent) into one of 4 strata. Even if pain is well controlled/resolved at present the patient will be considered positive for bone pain. The patient will then be randomized to Arm A or Arm B using the stratum-appropriate randomization list prepared in advance by the study statistician [name]. Arms A and B are defined in the Study Schema (on page 5) and in Section 5.3 below. Each of the 4 randomization sequences will use random permuted blocks of varying sizes. The treatment arm randomization and enrollment confirmation will be communicated to site staff in writing within 24-48 hours from receipt of all eligibility source documents. Study treatment should start within 7 days of registration.

5.3 Study design and plan:

Overall Study Design and Plan

This study is a multicenter Phase II, randomized, screening study of oral MDV3100 (160 mg/day) in patients with metastatic hormone sensitive prostate cancer. Patients must not have received prior cytotoxic chemotherapy for metastatic disease. Radiation therapy, and initiation of

bisphosphonates or other approved bone targeting agents, and standard of care steroid and pain management are allowed and should not result in discontinuation of study drug therapy.

For patients eligible for late induction registration the treatment start date will be the date of initiation of GNRH analogue or antagonist, with or without antiandrogen. Late induction patient visits will be adjusted based on the length of their prior hormone therapy. Study drug therapy should be continued as long as the patient is tolerating the study drug and continues androgen deprivation therapy or until confirmed radiographic disease progression or a skeletal related event AND one of the two following events: 1) initiation of another agent for treatment of prostate cancer. Or 2) Intolerance to therapy.

Patients will be randomized to receive either:

ARM A

Orchiectomy/LHRH analogue Leuprolide or Goserelin or any other FDA approved preparation, approved by PI on notification, except GNRH antagonist such as Degarelix) If patients are late induction and have started on degarelix (Firmagon;Ferring pharmaceuticals) or any GNRH antagonist they will need to be switched to a GNRH analogue.

and

Enzalutamide 160 mg (4Caps of 40 mg each) orally daily (experimental arm)

OR

ARM B

Orchiectomy/LHRH analogue Leuprolide or Goserelin or any other FDA approved preparation, approved by PI on notification, except GNRH antagonist such as Degarelix)

If patients are late induction and have started on degarelix(Firmagon;Ferring pharmaceuticals) or any other GNRH antagonist they will need to be switched to a LHRH/GNRH analogue.

and

Bicalutamide 50 mg orally daily (standard arm).

Stratification by ethnic origin (African American or other) and bone pain (Yes/No).

Patients should continue on study therapy after month 7 unless any of the criteria in section 9.0 for withdrawal are met

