PI- [name] Assistant Professor of Medicine
UAB Comprehensive Cancer center
[name]
[name]
[contact]
[contact]
Email: [contact]

Mount Sinai School of Medicine PI-

[name].
Chief, Division of Hematology and Medical Oncology Professor of Medicine and Urology [name] Professor in Clinical Cancer Therapeutics Icahn School of Medicine at

Mount Sinai Associate Director of Clinical Research The Tisch Cancer Institute
[name]

[contact] |
[contact]| patient
line [contact]

E Mail: [contact]

**Title: Phase II randomized trial of enzalutamide/MDV-3100 and LHRH analogue vs
combined androgen deprivation (LHRH analogue + bicalutamide) in metastatic hormone
sensitive prostate cancer**

| | |
|--|----|
| STUDY SCHEMA | 6 |
| 1.0 OBJECTIVES | 7 |
| 2.0 BACKGROUND | 7 |
| 3.0 DRUG INFORMATION | 12 |
| 4.0 ELIGIBILITY CRITERIA..... | 19 |
| 5.0 TREATMENT PLAN | 21 |
| 6.0 TOXICITIES TO BE MONITORED AND DOSAGE MODIFICATION..... | 23 |
| 7.0 STUDY CALENDAR..... | 25 |
| 8.0 CRITERIA FOR EVALUATION AND ENDPOINT DEFINITION | |
| ...26 | |
| 9.0 CRITERIA FOR REMOVAL FROM STUDY | |
| ...30 | |
| 10.0 CORRELATIVE STUDIES | |
| ...30 | |
| 11.0 STATISTICAL CONSIDERATIONS | |
| ...35 | |
| 12.0 ADVERSE EVENTS REPORTING..... | 40 |
| 13.0 REFERENCES..... | 47 |

| | |
|---|----|
| 14.0 DATA AND SAFETY MONITORING PLAN..... | 51 |
| 15.0 APPENDICES..... | 52 |
| STUDY SCHEMA | |

Non castrate metastatic prostate cancer
≤3 months of androgen deprivation for metastatic disease
At least 6 months since prior androgen deprivation therapy

PS - 0 - 2,
Adequate marrow, hepatic & renal function
No history of seizures or risk factors for seizures

STRATIFY by race (African American or Other) and by bone pain (yes or no)
(yields 4 strata)

R A N D O M I Z E within strata

Arm A
LHRH analogue
LHRH analogue
+
Enzalutamide
160 mg orally daily

Arm B
+
Bicalutamide
50 mg orally daily

DETERMINE PRIMARY ENDPOINT:

% of patients achieving a PSA nadir of ≤ 4 ng/ml at month 7
(Patients should continue on study therapy after month 7 unless any of the criteria in section 9.0 for withdrawal are met)

1.0 OBJECTIVES:

Primary objective:

To compare the rates of achieving PSA remission at month 7 with LHRH analogue therapy and enzalutamide (Arm A) with that achieved with LHRH analogue and bicalutamide (Arm B) in metastatic hormone sensitive prostate cancer .

Secondary Objectives:

- 1) To compare the primary endpoint by race.

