As enzalutamide inhibits the gamma amino butyric acid (GABA)-gated chloride channel, convulsion potential was assessed in single- and multiple-dose studies in mice. Oral therapy daily for 7 days was associated with convulsions in a dose-dependent manner with doses \geq 200 mg/kg being active. When administered as a single dose of 400 mg/kg the treatment was also associated with convulsions. At the highest dose at which no convulsions occurred (single dose, 100 mg/kg), the maximum plasma concentration (Cmax) and area under the curve at 24 hours after dosing (AUC24) were at least 2.5-times higher than those in patients receiving 160 mg/day. The incidence of seizures was noted in 0.6% of the patients treated in the registration trial. 5 of 800 patients experienced seizures on enzalutamide therapy and none on placebo therapy. The seizures were reversible after therapy was discontinued [5]. One case of status epilepticus (confusion associated with partial complex-status epilepticus) required medical intervention; the four other seizures were self-limited and did not recur after study-drug discontinuation. Four of the seizures were witnessed. Potentially predisposing factors were present in several patients. Two patients had brain metastases, 1 of whom had a seizure reported 26 days after the last dose of enzalutamide. One patient had inadvertently been administered lidocaine intravenously immediately before the seizure, and 1 patient with brain atrophy had an unwitnessed event classified as a seizure, in the context of a history of heavy alcohol use, after initiation of haloperidol 7 days beforehand. One additional adverse event reported by the investigator as syncope had several features suggestive of seizure. The enzalutamide group had a lower incidence of adverse events of grade 3 or above (45.3%, vs. 53.1% in the placebo group). The median time to the first such adverse event was 12.6 months in the enzalutamide group, as compared with 4.2 months in the placebo group. There was a higher incidence of all grades of fatigue, diarrhea, hot flashes, musculoskeletal pain, and headache in the enzalutamide group than in the placebo group. Cardiac disorders were noted in 6% of patients receiving enzalutamide and in 8% of patients receiving placebo (with cardiac disorders of grade 3 in 1% and 2%, respectively). Hypertension or increased blood pressure was observed in 6.6% of patients in the enzalutamide group and 3.3% of those in the placebo group.

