In a drug-drug interaction trial in healthy volunteers, a single 160 mg oral dose of XTANDI was administered alone or after multiple oral doses of gemfibrozil (strong CYP2C8 inhibitor). Gemfibrozil increased the AUC_{0-inf} of enzalutamide plus N-desmethyl enzalutamide by 2.2-fold with minimal effect on C_{max}.

In a drug-drug interaction trial in healthy volunteers, a single 160 mg oral dose of XTANDI was administered alone or after multiple oral doses of itraconazole (strong CYP3A4 inhibitor). Itraconazole increased the AUC_{0-inf} of enzalutamide plus N-desmethyl enzalutamide by 1.3-fold with no effect on C_{max}. The effects of CYP2C8 and CYP3A4 inducers on the exposure of XTANDI have not been evaluated *in vivo*.

CLINICAL STUDIES

The efficacy and safety of XTANDI in patients with metastatic castration-resistant prostate cancer who had received prior docetaxel-based therapy were assessed in a randomized, placebocontrolled, multicenter phase 3 clinical trial. The primary endpoint was overall survival. A total of 1199 patients were randomized 2:1 to receive either XTANDI orally at a dose of 160 mg once daily (N = 800) or placebo orally once daily (N = 399). All patients continued androgen deprivation therapy. Patients were allowed, but not required to continue or initiate glucocorticoids. Study treatment continued until disease progression (evidence of radiographic progression, a skeletal-related event, or clinical progression), initiation of new systemic antineoplastic treatment, unacceptable toxicity, or withdrawal. Patients with a history of seizure, taking medicines known to decrease the seizure threshold, or with other risk factors for seizure were not eligible

The following patient demographics and baseline disease characteristics were balanced between the treatment arms. The median age was 69 years (range 41-92) and the racial distribution was 92.7% Caucasian, 3.9% Black, 1.1% Asian, and 2.1% Other. Ninety-two percent of patients had an ECOG performance status score of 0-1 and 28% had a mean Brief Pain Inventory score of ≥ 4 . Ninety-one percent of patients had metastases in bone and 23% had visceral involvement in the lung and/or liver. Fifty-nine percent of patients had radiographic evidence of disease progression and 41% had PSA-only progression on study entry. All patients had received prior docetaxel-based therapy and 24% had received two cytotoxic chemotherapy regimens. During the trial, 48% of

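### The Schema bars seizure risk factors, but exclusion 1 in Section 4.2 does not carry this through to current use of medicines that lower the seizure threshold

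*Combined protocol and SAP*

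**What the plan says.** Four places bear on entry and on-study use.

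- **Study Schema.** The summary entry conditions include "No history of seizures or risk factors for seizures".
- **Section 4.2, exclusion 1.** The operative criterion reads "History of seizure or any condition that may predispose to seizure (e.g., prior cortical stroke, significant brain trauma) at any time in the past". A second sentence adds loss of consciousness or transient ischaemic attack in the 12 months before Day 1. No medicine is mentioned.
- **Section 3.1, Clinical Studies.** Of the registration trial it says: "Patients with a history of seizure, taking medicines known to decrease the seizure threshold, or with other risk factors for seizure were not eligible".
- **Section 3.1, Patient Counseling Information.** Staff are to tell patients about the seizure risk and to talk through both predisposing conditions and threshold-lowering medications.

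Section 2.0 gives the seizure experience in the registration trial: "The incidence of seizures was noted in 0.6% of the patients treated in the registration trial", that is, 5 of 800 on enzalutamide and none on placebo. Section 6.0 requires permanent discontinuation of enzalutamide after any reported seizure activity. Appendix A gives drug-interaction guidance limited to pharmacokinetic effects.

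**The concern.** The Schema states a general rule and Section 4.2 is where that rule should become checkable. Seizure history and predisposing conditions are carried across, but current medication is not. A site working through the numbered criteria could find that a patient taking a threshold-lowering medicine meets all of them unless the investigator chooses to invoke a discretionary clause.

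What is at stake is patient safety. Enzalutamide has a stated seizure hazard: Section 2.0 describes its action on the GABA-gated chloride channel, dose-dependent convulsions in mice, and seizures on active treatment only. Whether a patient with this added risk factor can be allocated to enzalutamide should not depend on how an investigator reads a one-line summary. In addition, Section 5.1 limits submitted concomitant-medication data to bisphosphonates and denosumab, so the routine trial data would not show who was taking such a medicine.

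**Working it through.** This is a question of wording, so the main check sets the sections side by side.

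**1. Are these medicines a seizure risk factor in the protocol's own terms?** In the Section 3.1 sentence, seizure history and threshold-lowering medicines are followed by a residual category introduced by the word *other*. That wording places the medicines within the class of risk factors. The Schema bars that class in general terms.

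**2. Does exclusion 1 reach them?** Its object is a history or a condition, its examples are cortical stroke and brain trauma, and its time frame looks back over the past. The counselling text in Section 3.1 lists conditions and medications as two separate items. A current prescription is therefore not clearly a condition in the sense of exclusion 1.

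**3. Does any other criterion reach them?** Section 4.1 has 14 inclusions and Section 4.2 has 19 exclusions; none names these medicines. The nearest are discretionary: exclusion 16 (undue risk in the investigator's opinion), and exclusion 3 or inclusion 6 where the underlying illness is serious enough.

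**4. What applies after entry?** The counselling text is addressed to the patient. Appendix A deals with enzyme and transporter interactions, not with additive effects on seizure threshold. Section 5.3 lists some permitted supportive treatments and is silent on this class.

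**5. Can the gap be sized?** The only relevant figure reproduces: 5/800 = 0.00625 = 0.625%, stated as 0.6%. It comes from a trial that excluded users of these medicines at entry. An excess rate would need the seizure rate in users and the number of users likely to enrol. The documents give neither.

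**6. Do the individual cases help?** Section 2.0 says "Potentially predisposing factors were present in several patients" and describes four:

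- "Two patients had brain metastases, 1 of whom had a seizure reported 26 days after the last dose of enzalutamide". Exclusion 2 already bars brain metastases here.
- "One patient had inadvertently been administered lidocaine intravenously immediately before the seizure".
- A patient with brain atrophy had an unwitnessed event "in the context of a history of heavy alcohol use, after initiation of haloperidol 7 days beforehand".

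A medicine is named in 2 of 5 seizures (exact 95% interval 5.3% to 85.3%). If the four described cases are separate patients, 5 − 2 = 3 seizures fall outside brain metastases and a medicine is named in 2 of these 3 (9.4% to 99.2%). Intervals this wide carry no usable information. Both exposures also came after trial entry, so an entry rule would have prevented neither.

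**7. Does a design figure change?** Section 11.5 uses 50% versus 75%, one-sided alpha 0.10 and power 0.80. Recomputing with the continuity correction gives 41 per arm, and 41/(1 − 0.10) = 45.6, rounded up to 46. Both match the protocol, and neither depends on the wording of exclusion 1.

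**The case against.** The strongest reply is that the protocol already bars these patients. Read together, the Schema line and Section 3.1 exclude them. Exclusion 16 extends to any reason that puts a patient at undue risk, so it is not confined to conditions. Eligibility is verified centrally before treatment under Section 5.1. This partial cover is real, and a reader who inferred that current users enter unguarded would go further than the documents allow. What remains is that the Schema is a summary, exclusion 16 is opinion with no list or washout, and central verification has no numbered criterion prompting it to look for these medicines.

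A second reply is that the registration trial's criteria do not bind this one, and that the counselling text handles these medicines by discussion. That is also correct. The point does not rest on copying another trial's criterion. It rests on this protocol's own Schema, with Section 3.1 showing what the protocol counts as a risk factor.

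A third reply is that other exclusions naming drugs (9 and 15) mainly concern hormonal or PSA-lowering agents, so silence on this class does not show an intention to admit it. I agree, and draw no such inference.

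Finally, a reader might infer that the protocol ignores the issue during treatment. It does not: patients are counselled on such medicines, and any seizure activity ends enzalutamide. The gap is narrower, namely that the prescriber is given no caution against starting one.

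**Conclusion.** The point stands as an internal mismatch with a safety consequence: Section 4.2 does not put into effect, for current medication, the risk-factor exclusion that the Schema states. Its size cannot be given as a rate. The effect on the primary endpoint is likely negligible, and the sample size is untouched. It is a worthwhile low-cost improvement, not a flaw that undermines the trial.

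The conclusion assumes that the Schema line is meant as an entry rule and that the Section 3.1 sentence is a fair guide to what it covers.

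Two stronger readings are tempting and should be set aside. One is that the registration-trial seizures show that an entry rule is needed. The counts are too few, the lidocaine was inadvertent, the haloperidol patient had brain atrophy and heavy alcohol use, and both exposures followed entry. At most, the haloperidol case illustrates why an on-treatment caution is sensible. The other is that the protocol understates risk by applying 0.6% to users of these medicines. It never does so: Section 2.0 attributes that figure only to patients treated in the registration trial.

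**What to change.** 1. **Section 4.2, exclusion 1.** Extend it to other seizure risk factors, expressly including current use of medicines known to lower the seizure threshold. The sponsor's medical lead should set the list and the washout before entry.
2. **Section 5.3 or Appendix A.** Add a caution to prescribers against starting such medicines while a patient is on enzalutamide.

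With the first change, Section 4.2 matches the Schema. If the sponsor instead intends to admit these patients with counselling alone, Section 4.2 should say so and the Schema line should be narrowed to agree.

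The cost is about one line in each place. A few otherwise eligible patients would be excluded (the number cannot be estimated from the documents), and because eligibility precedes randomisation the entry rule would apply to both arms. The caution would narrow some prescribing choices in Arm A. The sample size and the analyses need no change.
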